6.1.2 Sensitivity Analyses

The main analysis is based on the “Main analysis set”, which do not include patients for whom the primary endpoint is missing. This choice is thought to be conservative as it is considered very unlikely that a patient with sequelae at 6-months would not attend the follow-up visit at 6-months.

³Note that the `uncondExact2x2` function guarantees compatible inference via either confidence interval or p-values, so concluding based on the p-value or the confidence interval is fully equivalent here (unlike when using some other software/methods).

This is especially unlikely as telephone interviews focusing on signs of sequelae were planned for all patients not attending the 6 month follow-up.

Nevertheless, we will perform the following sensitivity analysis, for completeness. We will report the results (p-value and upper limit of the 97.5% CI) for all possible combinations of the values of missing outcomes in the OT and IVT groups. An graphical representation similar to the “Enhanced tipping-point display” presented in Liublinska et al. [9, Fig. 2] will be reported, to provide an overview of the results. It will show a heat map of the upper limit of the 97.5% CI (or p-value) for each possible combinations.

As it is considered very unlikely that a patient with sequelae at 6-months would not attend the follow-up visit at 6-months, the results of the sensitivity analysis assuming that none of the patients with missing data had sequelae will be of special interest.

6.1.3 Supplementary analysis: principal stratum estimand

The following clinical question is also of interest: *“Is the risk of having sequelae 6 months after BJI not more than 5% larger when initiating high-dose OT as compared to IVT, regardless of initiation of any additional interventions during the follow-up, in the principal stratum of patients who will never need to switch treatment (from OT to IVT or the other way around) to ensure good clinical care?”*

The corresponding “principal stratum” estimand is described by the following attributes:

- Population: subgroup of population of the primary estimand (See Section 3.1.1), which includes only patients who will never need to switch treatment (from OT to IVT or the other way around) to ensure good clinical care.
- Endpoint: same as for the primary estimand (Sec. 3.1.1)
- Treatment: same as for the primary estimand (Sec. 3.1.1)
- The intercurrent event “treatment switch (from OT to IVT or the other way around)” is addressed by the population of interest attribute (“Principal stratum strategy”, see [7]) and “any other subsequent treatment decision needed to ensure good clinical” is addressed by the treatment condition of interest attribute (“treatment policy strategy”, see [7]).
- Population-level summary: same as for the primary estimand (Sec. 3.1.1)

Rationale for considering this estimand: First, it was the analysis that the main investigators had in mind when referring to the “per-protocol” analysis in the protocol paper [11]. As this analysis was pre-specified in the protocol, it should be performed, hence it is included in this SAP. Second, this is a non-inferiority study and of course a lot of treatment switching could be suspected to make the results of the two groups more similar, increasing the chance of showing non-inferiority. However, fundamentally the research hypothesis of this project is that high-dose OT is non inferior to IVT in the way the antibiotics are processed by the patient, hence giving similar clinical outcomes. Third, it could be hypothesized that some subgroups of patients (e.g., teenager vs young children) are more or less prone to treatment switching (e.g., from OT to IVT due to vomiting). Therefore, the results of the principal stratum analysis could provide reasonable estimates of the results that could be expected in such subgroups (to some extent).

For the corresponding statistical analysis, we will proceed as for the main analysis detailed in Section 6.1.1, except that the “Principal stratum analysis set” will be used instead of the “Main analysis set”.

The rationale for this statistical analysis is the following. Although it is generally agreed that “*the subset of subjects who experience an intercurrent event [treatment switch in our study] on the test treatment will often be a different subset from those who experience the same intercurrent event on control*”; and therefore that “*Treatment effects defined by comparing outcomes in these subsets confound the effects of the different treatments with the differences in outcomes possibly due to the differing characteristics of the subjects.*” [7], we do not believe that this is the case in our study. Therefore, we do not suspect the planned analysis to be biased. The rationale behind this is the following.

Let Y and S denote the outcome and indicator of treatment switch, respectively, and Y^x and S^x the corresponding counterfactuals for each intervention $x = 0$ (IVT) and 1 (OT); we expect

$$\underbrace{E(Y^1 - Y^0 | S^0 = S^1 = 0)}_{\text{principal stratum estimand}} = \underbrace{E(Y^1 | S^1 = 0) - E(Y^0 | S^0 = 0)}_{\text{estimand of subset analysis}}$$

simply because

$$E(Y^1 | S^0 = S^1 = 0) = E(Y^1 | S^1 = 0) \quad (1)$$

$$\text{and } E(Y^0 | S^0 = S^1 = 0) = E(Y^0 | S^0 = 0) \quad (2)$$

Assumption (1) above is fulfilled if the risk of sequelae is the same among patients randomized to OT who will never switch to IVT, regardless of whether they would have switched to OT if they had been randomized to IVT. Similarly, Assumption (2) is fulfilled if the risk of sequelae is the same among patients randomized to IVT who will never switch to OT, regardless of whether they would have switched to IVT if they had been randomized to OT. We believe these assumptions reasonable as the main reasons for switching (e.g, vomiting that prevents OT) do not seem to share a common cause with the outcome of interest (sequelae); or, at least, not a common cause which has a non-negligible effect on the outcome.

6.2 Secondary Endpoints Analyses

The main statistical analysis for the secondary outcomes and estimands defined in Section 3.1.2 will be similar to that of the primary outcome defined in Section 6.1.1, except that:

- we will compute a two-sided 95%-CI instead of a one-sided 97.5%-CI and we will not compute an accompanying p-value (see appendix 8.3 for the specific R code that we will use).
- we will use the “Secondary outcomes analysis set” instead of the “Main analysis set” (see details of the sets in Section 5).

The change of analysis set is because we want to use as much data as possible for the analyses and because we cannot think of any reason why a missing follow-up at 6 months (i.e., a missing primary outcome) should lead to excluding a patient for the secondary outcome analyses. For the same reason, we will proceed similarly for the tertiary (safety and exploratory) outcomes (see section 6.3).

6.3 Tertiary (safety and exploratory) Endpoints Analysis

We will also analyze the following Safety (**S**) and Exploratory (**E**) outcomes listed below. The information in parenthesis at the end of the description of each outcome refers to the statistical methods that will be used to analyze them, which is described below. Note that S1–S3 and E1–E5 were already listed in Table 1 in the protocol paper [11].

S1: severe complications during antibiotic treatment within 28 days. E.g., need for intensive care, septic shock, organ failure, pyomyositis, endocarditis, deep venous thrombosis. (**B + TTE**)

S2: need for surgical intervention during antibiotic treatment within 28 days; excluding diagnostic surgical intervention (diagnostic joint aspiration or diagnostic bone biopsy). (**B + TTE**)

S3: non-severe treatment-related adverse events within 3 months. E.g., complications of intravenous access (infection, need for replacement, extravasation) and drug side effects reported by medical staff, patients or parents (electronic questionnaire). (**B + TTE**)

E1: time from initiation of antibiotic treatment to apyrexia within 28 days, as reported by the patients or parents. Apyrexia will be defined by a temperature $< 38^{\circ}\text{C}$ for 24 hours. Patients or parents were asked to report the temperature three times per day (until apyrexia). (**KM**)

E2: total duration of antibiotic therapy within 3 months. (**Q + TTE**)

E3: sequelae within 12 months. E.g., abnormal mobility and growth abnormalities, assessed by clinical examination by a qualified pediatrician 12 months after the initiation of treatment, accepted range 11–14 months. (**B**)

E4: radiological abnormalities within 12 months. It is assessed by a qualified radiologist 12 months after initiation of treatment, accepted range 11–14 months. (**B**)

E5: secondary infection with antimicrobial-resistant organisms or *Clostridioides difficile*, within 3 months. (**B**)

E6: discontinuation of the randomized treatment strategy within 28 days. (**B + TTE**)

E7: early termination of falsely included patient within 6 months (i.e., suspicion of infection is abandoned). (**B + TTE**)

E8: time to shift to 'follow-up treatment' after clinical improvement (pain and mobility) and paraclinical improvement (decreasing C-reactive protein) within 3 months. (**Q + TTE**)

E9: duration of 'follow-up treatment' within 3 months (Note: E8+E9= E2). (**Q + TTE**)

We prespecify the analysis sets and the statistical methods that will be used to analyze each of the above Safety and Exploratory outcomes as follows. Additional (post hoc) exploratory analyses might be performed.

Analysis sets. For the analyses of outcomes S1, S2, S3 and E7 we will use the "All participants analysis set", whereas we will use the "Secondary outcomes analysis set" for outcomes E1–E2 and E5–E6 and E8–E9 and the "Long-term outcomes analysis set" for outcomes E3–E4. This information is summarized in Table 6.3.

Outcome	Analysis set				
	“Main”	“Second”	“All”	“Late”	“PS”
Primary	X				X
S1			X		
S2			X		
S3			X		
E1		X			
E2		X			
E3				X	
E4				X	
E5		X			
E6		X			
E7			X		
E8		X			
E9	X				

Note: “Main”, “Second”, “All”, “Late” & “PS” stand for “Main analysis set”, “Secondary outcomes analysis set”, “All participants analysis set”, “Long-term outcomes analysis set” and “Principal stratum analysis set”.

Table 1: Analysis sets for each outcome.

Binary outcomes analyses (B). Outcomes S1–S3, E3–E7 are binary outcomes. They will be analyzed using the same statistical method as for the primary outcome, except that we will compute a two-sided 95% CI instead of a one-sided 97.5% and that no p-value will be computed (see appendix 8.3 for the specific R code that we will use).

Time-to-event analyses (TTE). Outcomes S1–S3, E1–E2 and E6–E9 are –or can also be analyzed as– time to event outcomes. They will be analyzed by estimating (and plotting) the cumulative incidence/risk function within each treatment arm, with pointwise two-sided 95%-CI. That is, we will present the proportion of event observed before day t , for $t = 0, 1, 3, \dots$ for each treatment arm and the corresponding exact binomial two-sided 95% CIs (computed using the `binom.test()` function of R). This simple analysis is planned because we expect no censoring.

Quantitative outcomes analyses via quantiles (Q). Outcomes E2, E8 and E9 are quantitative outcomes (duration). They will (also) be analyzed by estimating the median within each treatment arm and their difference, together with two-sided 95%-CIs. The CI will be computed using non-parametric BCa Bootstrap (using $B=10,000$ replicates, via the R packages `boot` and `simpleboot`, see appendix 8.2 for the specific R code that we will use).

Kaplan-Meier analysis (KM). Outcome E1 is a time-to-event outcome (time to apyrexia). It will not be fully observed for all patients due to missing data, which will lead to censored observations. Hence we will use the Kaplan-Meier method to compute the “survival curves” for the event “apyrexia” within each group. We will define the time to apyrexia as the time to the third consecutive recording (observed or imputed) with a temperature $< 38^{\circ}\text{C}$ (i.e., approximately 24h with a temperature below 38°C). Missing temperature recordings will lead to imputation or censoring as follows. Last observation carried forward will be applied to impute up to two consecutive missing temperature recordings. If more than two consecutive recordings are missing, we will censor the

time to apyrexia at the time of the third consecutive missing temperature (the first time three consecutive temperatures are missing, if this happens several times). The `prodlim` package of R will be used to compute the Kaplan-Meier curves in each arm with pointwise two-sided 95%-CI. The corresponding median survival time in each arm and their difference will also be computed, also with two-sided 95%-CI, computed using non-parametric BCa Bootstrap (using $B=10,000$ replicates, via the R packages `boot` and `prodlim`, see appendix 8.4 for the specific R code that we will use).

Further remarks: for the outcome E6 (discontinuation of the randomized strategy), data about the reason for discontinuation have been collected. Additional (post hoc) exploratory analyses of these additional data will be performed too.

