3.1 Objectives, Endpoints, and Estimands

3.1.1 Primary

The primary objective is to show that initial high-dose Oral Treatment (OT) is not inferior to initial IntraVenous Treatment (IVT) with respect to the risk of sequelae after 6 months. A non inferiority margin of 5% difference in risk was pre-specified. Accordingly, the primary outcome is the presence of abnormal mobility or function of the affected joint/bone at 6 months follow-up, as evaluated by a blinded clinical examination by a qualified clinician.

Specifically, the two interventions being investigated are initiating either OT or IVT and continuing the treatment until the first of these two events occurs:

- clinical improvement (pain and mobility) and paraclinical improvement (decreasing C-reactive protein) or 3 days (whichever comes last)
- OT or IVT is no longer compatible with good clinical care (e.g. insufficient clinical effect of either OT or IVT, the patient/child is not accepting or tolerating OT or IVT.)

After this initial treatment duration, a follow-up treatment using OT with reduced dose is planned for 1 week in case of joint infection only, 4 weeks in case of spondylodiscitis and 3 weeks in case of other bone infections.

The primary clinical question of interest is: *“Is the risk of having sequelae 6 months after BJI not more than 5% higher when initiating high dose OT as compared to IVT, regardless of initiation of any additional interventions during the follow-up, including switching treatment (from OT to IVT or the other way around), when needed to ensure good clinical care?”*

Accordingly, the primary estimand is described by the following attributes:

- Population: Children and adolescents (3 months to 18 years) with suspicion of first uncomplicated BJI, possibly already treated with either OT or IVT for up to 24h and for whom the suspicion of BJI will not be abandoned within 6 months.
- Endpoint: Presence of an abnormal mobility or function of the affected joint/bone at 6 months follow-up, as evaluated by a blinded clinical examination by a qualified pediatrician and/or pediatric orthopedic surgeon.
- Treatment: The investigational interventions (initiating high-dose OT vs IVT) regardless of any subsequent treatment decision needed to ensure good clinical care (“treatment policy strategy”, see [7]).

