Another important remark also needs to be made, about the rationale for how we deal with the intercurrent event “the suspicion of BJI is abandoned”. Although it is generally agreed that “*the subset of subjects who experience an intercurrent event [here: suspicion of BJI is abandoned] on the test treatment will often be a different subset from those who experience the same intercurrent event on control*”; and therefore that “*Treatment effects defined by comparing outcomes in these subsets confound the effects of the different treatments with the differences in outcomes possibly due to the differing characteristics of the subjects.*” [7] (see also [2] for similar discussions); we do not believe that this is the case in our study (as already mentioned above, in the remark at the end of Section 3.1.1). Therefore, we do not suspect the planned analysis to be biased. Indeed, we think that for each patient for whom the suspicion of BJI is not abandoned, it would not have been abandoned either if the child had been randomized to the other treatment arm. This seems reasonable as the main reason to abandon the suspicion (imaging, blood samples or clinical follow-up reveals another diagnosis) is not expected to be a consequence of the received intervention (OT or IVT). However, in the rare case where the diagnosis remains uncertain, there is a small risk that the treating clinician could abandon the diagnosis of BJI (and thereby ending the antibiotic treatment) in the IVT group more often than in the OT group. This is because IVT is more invasive than OT and therefore the incentive to stop IVT could be stronger than the incentive to stop OT, in case of doubt about the BJI diagnosis. We believe this risk to be negligible and it has been accepted in the overall design of the study, as a minor limitation.

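### Safety outcomes S1 and S2 count events only while the child is on antibiotics, so their nominal 28-day window closes early for many children, by an amount set after randomisation

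*SAP*

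**What the plan says.** Section 6.3 attaches two conditions to each of the first two safety outcomes: "S1: severe complications during antibiotic treatment within 28 days" and "S2: need for surgical intervention during antibiotic treatment within 28 days", the latter excluding diagnostic procedures. The third has a fixed window and no on-antibiotics condition: "S3: non-severe treatment-related adverse events within 3 months".

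S1 and S2 are analysed in the All participants set, both as risk differences and as the cumulative proportion with an event by each day. On the second method the SAP remarks: "This simple analysis is planned because we expect no censoring".

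Time on antibiotics is described in section 3.1.1. For a child who improves, the initial phase lasts until improvement or 3 days, whichever is later. Afterwards, "a follow-up treatment using OT with reduced dose is planned for 1 week in case of joint infection only"; the course is 3 weeks for other bone infections and 4 weeks for spondylodiscitis. Section 6.1.1 adds that abandoning the diagnosis ends antibiotics. It allows that, in rare uncertain cases, clinicians could "abandon the diagnosis of BJI (and thereby ending the antibiotic treatment) in the IVT group more often than in the OT group", and it regards this risk as negligible.

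No rule says how to classify an S1 or S2 event that occurs after antibiotics stop, or after they are restarted, but before day 28.

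**The concern.** The label suggests a 28-day safety outcome in all randomised children. The definition gives something else: a child whose course ended on day 10 and who has septic shock or a drainage operation on day 14 is scored as event-free, at least if antibiotics had not been restarted first.

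Two things are at stake. First, S1 and S2 are the only listed outcomes for severe complications and for therapeutic surgery, and they do not see such events once treatment has ended. Second, the length of each child's window is determined after randomisation, by speed of improvement, type of infection and whether the diagnosis is kept. If time on antibiotics differs between arms, the S1 and S2 risk differences compare unequal times at risk.

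**Working it through.** The SAP gives no sample size, power or expected rate for S1 or S2, so there is no figure of its own to reproduce. The check is of window length and of coverage by other outcomes.

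**Inputs (section 3.1.1).** The initial phase is at least 3 days for a child who improves; values above 3 are assumptions. Follow-up courses are 7 days (joint only), 21 days (other bone) and 28 days (spondylodiscitis).

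**Formula.** Stop day = initial phase + follow-up course. Uncounted days = 28 − min(28, stop day).

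| Infection | 3-day phase | 5-day (assumed) | 7-day (assumed) | 14-day (assumed) |
|---|---|---|---|---|
| Joint only | stop 10, uncounted 18 (64%) | stop 12, 16 (57%) | stop 14, 14 (50%) | stop 21, 7 (25%) |
| Other bone | stop 24, uncounted 4 (14%) | stop 26, 2 (7%) | stop 28, 0 | stop 35, 0 |
| Spondylodiscitis | stop 31, uncounted 0 | stop 33, 0 | stop 35, 0 | stop 42, 0 |

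For an abandoned diagnosis with antibiotics stopped on day d, 28 − d days are uncounted; if d = 3 (assumed), that is 25 days.

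**Share of child-days over a mix.** Let q be the assumed proportion with joint infection only, the rest having other bone infection.
- 3-day phase: q × 18/28 + (1 − q) × 4/28. For q = 20%, 40%, 60% this gives 24%, 34%, 44%.
- 7-day phase: q × 14/28. This gives 10%, 20%, 30%.

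Any children with spondylodiscitis would lower these shares.

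**What unequal windows can do (illustration only).** Assume joint infection only, the same constant hazard in both arms and a true 28-day risk of 5%. Counted risk = 1 − 0.95^(stop day/28).
- Stop on day 10: 1 − 0.95^(10/28) = 1.8%.
- Stop on day 14: 1 − 0.95^(14/28) = 2.5%.

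An arm with a 3-day and an arm with a 7-day initial phase would differ by about 0.7 percentage points with no true effect. None of these inputs is an SAP estimate.

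**Coverage elsewhere.**
- Recurrence within 6 months (section 3.1.2) captures same-site relapse after treatment that needs more antibiotics. It does not record whether the event was, say, septic shock, thrombosis or surgery.
- Treatment failure within 28 days, sequelae at 6 and 12 months and 12-month radiology are not limited to time on antibiotics. They do not record severe complications or surgery as such.
- All of these use analysis sets that exclude children whose diagnosis was abandoned (section 5).
- S3 includes abandoned children but covers only non-severe events.

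A severe complication or therapeutic surgery after abandonment, once antibiotics have stopped, is therefore in no listed outcome, although S1 and S2 use the All participants set.

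**The case against.** The strongest reply is that the definition is inherited. The SAP says that S1 to S3 were listed in the protocol paper, which is not shown here and may refine the window or deal with restarted antibiotics. An on-treatment count is a legitimate outcome, and nothing in the SAP contradicts it. This stands as a reason to keep that version, but not as a reason to report it alone.

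A reader might infer that harm after stopping is missed altogether. The documents do not support that: recurrence, treatment failure and sequelae cover much of what under-treatment would cause in children whose diagnosis stands, and they rank above or beside S1 and S2. The gap is the narrower one set out in the working.

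A reader might also infer that the window is shorter in the IVT arm. Section 6.1.1 raises unequal abandonment only as a small risk in rare uncertain cases and considers it negligible. The follow-up course depends on infection type, not on arm. A difference in the initial phase is possible, but its direction is unknown.

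Nor is the no-censoring remark a statistical fault. For an observed child, whether an on-treatment event has occurred by day t is fully determined, and a crude proportion estimates that quantity validly.

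Finally, data after early termination may be thin. E7 describes abandoned children as terminated early, and section 6.5 shows that data for another planned safety analysis were not collected. This stands, and it limits what can be promised for a fixed-window count.

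**Conclusion.** The point holds for S1 and S2 as worded. In joint infection, counting ends at the earliest around day 10, with 18 of 28 days uncounted at the 3-day minimum and 14 with an assumed 7-day phase. In other bone infection it is 4 days or 0, in spondylodiscitis none, and after abandonment the whole remainder. These figures assume that courses run as planned and that antibiotics are not restarted.

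They are shares of time, not of missed events; equating the two would need a flat hazard, which the SAP does not support. Dependence of the window on post-randomisation treatment is a real weakness of the arm comparison, but the documents give no basis for stating the direction or size of any bias.

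S1 and S2 are tertiary outcomes reported without p-values, so the non-inferiority conclusion is not affected. The change is worth making because these are the only listed outcomes for severe complications and surgery.

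**What to change.** - In section 6.3, report S1 and S2 as any severe complication, or any non-diagnostic surgical intervention, within 28 days of randomisation regardless of antibiotic status, in all randomised participants. Use this for the risk differences and the cumulative incidence curves.
- Show the protocol-listed on-treatment version alongside, and say whether events after a restart of antibiotics count in it.
- State by arm for how many children status to day 28 is known, separately for those terminated early.
- List the change in section 6.5.

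This concerns event counting only, not treatment. The cost is SAP wording, one extra derivation and a check of events in children terminated early. Some later events may be unrelated to treatment, and capture after early termination may be incomplete. If it is, the fixed-window result should be presented with that limitation.

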4.1 Multiplicity Adjustment

No multiple testing correction will be used, as formal hypothesis testing will be performed only for the primary endpoint/estimand described in Section 3.1.1, for the null hypothesis defined in Section 4.

Reporting for other endpoints/estimands will be limited to point estimates of effects with 95% (two-sided) confidence intervals. The widths of the intervals will not be adjusted for multiplicity and therefore it will not be possible to use them in place of formal hypothesis testing. This is in line with common recommendations [10].

5 Analysis Sets

- The “**Main analysis set**” consists of all randomized participants whose suspicion of infection is not abandoned during the study period and for whom the primary endpoint is not missing. The primary endpoint is missing if the patient did not attend the follow-up after 6 months. More precisely, it is missing if the patient did not attend the “6-month follow-up visit” between 5 and 9 months after randomization.
- The “**Secondary outcomes analysis set**” consists of all randomized participants whose suspicion of infection is not abandoned during the study period. That is, the dataset obtained after adding the patients who did not attend the follow-up after 6-months to the “Main analysis set”.
- The “**All participants analysis set**” consists of all randomized participants.
- The “**Long-term outcomes analysis set**” consists of all randomized participants whose suspicion of infection is not abandoned during the study period and for whom the “12 months follow-up” data are not missing. The “12 months follow-up” is missing if it did not happen between 11 and 14 months after randomization.
- The “**Principal stratum analysis set**” consists of all randomized participants whose suspicion of infection is not abandoned during the study period, for which the primary endpoint is not missing and who did not switch treatment during the initial treatment period following randomization (from OT to IVT or the other way around). That is, the set obtained after excluding from the “Main analysis set” the patients who switched during the initial treatment period.

6 Statistical Analyses

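### E5 (resistant-organism or C. difficile infection) is planned only in children whose BJI suspicion is never abandoned; an analysis in all randomised children should be added

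*SAP*

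**What the plan says.** Section 6.3 lists E5 as an exploratory binary outcome: "secondary infection with antimicrobial-resistant organisms or" C. difficile, with a 3-month window. It is to be reported as a risk difference with a two-sided 95% confidence interval and no p-value.

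The same section then allocates analysis sets. "For the analyses of outcomes S1, S2, S3 and E7 we will use the" All participants analysis set. The Secondary outcomes analysis set is used "for outcomes E1–E2 and E5–E6 and E8–E9". Table 1 marks E5 in the same column, so text and table agree.

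Section 5 defines the Secondary outcomes analysis set. It "consists of all randomized participants whose suspicion of infection is not abandoned during the study period. That is, the dataset obtained after adding the patients" (here, those with a missed 6-month visit). Every child whose suspicion of infection is abandoned is therefore outside it.

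A neighbouring outcome with the same window is handled differently. "S3: non-severe treatment-related adverse events within 3 months" is analysed in all randomised children.

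**The concern.** Most outcomes placed in the Secondary outcomes set describe the course or treatment of a real BJI, such as time to apyrexia or duration of follow-up treatment. Leaving out children who turn out not to have BJI is natural there. E5 is different. A resistant-organism or C. difficile infection can follow antibiotic exposure whether or not the child had BJI, and abandoned children can have been exposed. Section 6.1.1 describes abandonment as the act that ends antibiotic treatment.

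The exclusion is decided after randomisation, by clinicians who know the arm. For a harm that does not depend on the diagnosis, it gives up the comparison of the groups as randomised without an evident gain. It also means that E5 cannot be read beside S1–S3 on the same children. E5 is the only outcome in the SAP that names these infections.

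**Working it through.** The SAP gives no figure for this point, so there is nothing to reproduce. The check is a comparison of sections, followed by an illustration on assumed inputs.

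**Sections side by side**

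| Item | S3 | E5 |
|---|---|---|
| Label | Safety | Exploratory |
| Window | 3 months | 3 months |
| Requires BJI by definition | No | No |
| Analysis set | All participants | Secondary outcomes |
| Abandoned children included | Yes | No |

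1. *Is there a stated reason for the exclusion?* Section 6.2 explains why children with a missing 6-month visit are kept and extends that reasoning to the tertiary outcomes. It does not discuss abandoned children. The restriction on abandonment comes from the primary estimand (Section 3.1.1), which Section 3.1.2 carries over to the two secondary outcomes. No estimand is stated for E5.
2. *Is E5 planned in abandoned children anywhere else?* No section does so.
3. *Do S1 and S3 cover the gap?* Only in part. S1 is limited to severe complications during antibiotic treatment within 28 days, and S3 to non-severe treatment-related events. Neither names resistant-organism or C. difficile infection. A severe C. difficile infection that arises after antibiotics have stopped in an abandoned child fits neither definition.
4. *Timing.* E5 closes at 3 months, but Section 5 applies abandonment over the whole study period and E7 counts it to 6 months. A child with an E5 event in month 2 whose diagnosis is dropped in month 5 would be removed retrospectively.

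**Illustration (abandonment and E5 risk are assumed)**

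Section 7 sizes the trial at 180 children with confirmed BJI, 90 per arm, so abandoned children come on top.

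- Children left out if a fraction f of all randomised is abandoned and 180 are retained: 180 × f/(1 − f). For f = 10%, 180 × 0.10/0.90 = 20. For f = 40%, 180 × 0.40/0.60 = 120.
- With m abandoned per arm and E5 risk r among them, the expected number of events left out is 2mr, and the chance of leaving out at least one is 1 − (1 − r)^(2m):

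| m per arm | r | Expected events left out | Chance of at least one |
|---|---|---|---|
| 10 | 1% | 0.2 | 18% |
| 10 | 5% | 1.0 | 64% |
| 20 | 2% | 0.8 | 55% |
| 40 | 1% | 0.8 | 55% |
| 40 | 5% | 4.0 | 98% |

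- Effect of one event on an arm's exact two-sided 95% upper limit. With 0/90 (planned set) it is 1 − 0.025^(1/90) = 4.0%. If that arm's only event was in an abandoned child, the All participants result is 1/(90 + m). The limit is then the 97.5th percentile of Beta(2, n − 1) with n = 90 + m: 5.45% for n = 100, 4.96% for n = 110 and 4.21% for n = 130.

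**The case against.** The best defence is that the allocation follows a clear rule. Outcomes labelled as safety use all randomised children, as does E7, which could not be analysed otherwise. The remaining exploratory outcomes assessed before the 12-month visit use children whose suspicion was not abandoned. The SAP calls E5 exploratory, and the risk of these infections among children actually treated for BJI is a legitimate question. Abandoned children stop antibiotics early, so including them adds short exposures and pulls the arms together. E7 terms them early terminations, and the SAP does not say whether E5 was ascertained in them to 3 months. All of this stands. It argues for keeping the planned analysis, but not for having it alone, since the SAP already plans S3 over the same 3 months in all randomised children.

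Three stronger readings are tempting but not supported:

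- *That the SAP contradicts itself.* It does not. Text and table agree, and E5 is not labelled as safety. That it is a harm of antibiotic exposure is a reading of its definition.
- *That the SAP breaks its own aim of using as much data as possible.* That sentence in Section 6.2 concerns only children with a missing 6-month visit.
- *That the SAP admits uneven abandonment between arms.* Section 6.1.1 says that a clinician "could abandon the diagnosis of BJI (and thereby ending the antibiotic treatment) in the IVT group more often than in the OT group", but confines this to rare cases of doubtful diagnosis, calls the risk small and believes it negligible. The remark also concerns the primary analysis, not E5.

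**Conclusion.** The point holds as a cheap improvement. E5 is a harm that does not require BJI, yet its only planned analysis conditions on a post-randomisation decision that can even follow the event.

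The size cannot be fixed from the SAP. The figures above rest entirely on assumed abandonment and assumed risk, and the higher risks may be generous for children with short exposure. The likely effect is small. It matters mainly because E5 should be rare, so a single event can change how an arm looks. E5 carries no hypothesis test, and the non-inferiority conclusion is untouched.

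A reader might infer that such events vanish from the report altogether. That goes too far: S1 or S3 may capture some of them in all randomised children, and E7 will show how many children were abandoned per arm. Capture is not assured, because neither safety outcome names these infections.

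**What to change.** In the Section 6.3 text and in Table 1, assign E5 to the All participants analysis set, as for S1–S3. Keep the Secondary outcomes set result as a second line beside it. Report, per arm, how many abandoned children had E5 ascertained to 3 months, so that the reader can see whether their non-events were observed or presumed.

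The cost is one edit in the text, one in the table, one extra output line and a small count table. The downside is that shorter exposure and possibly incomplete ascertainment in abandoned children slightly dilute the absolute risk. The side-by-side result makes that visible.
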